Official Title: Application of Transcranial Alternating Current Stimulation for Modulation of Sleep and Cognitive Performance

NCT03112902

June 4th, 2019

TITLE: Application of transcranial alternating current stimulation for modulation of sleep and cognitive performance.

PROTOCOL VERSION DATE: 04June2019

COMIRB# 16-1875

PRINCIPAL INVESTIGATOR (PI):

Name: [name], PhD

Address: Department of Neurology

University of Colorado School of Medicine
[name]
[name]
[name]

[contact]

Email: [contact]

I. OBJECTIVES

Impaired sleep, in particular fragmented sleep and loss of slow wave activity (SWA) during non-rapid-eye-movement (NREM) sleep, is known to occur during the physiologic process of aging (1-3). Disrupted sleep is particularly pronounced among patients with diagnoses of Mild Cognitive Impairment (MCI) and those who progress to Alzheimer's Disease (AD), and is associated with worsening of cognitive impairment with progression of brain pathophysiology (4, 5). Recent advances in non-invasive neuromodulation via transcranial electric stimulation (tES) offer a chance for immediate impact on sleep and cognition, with a safe and readily available technology (6, 7). Neurophysiologic mechanisms of tES have been elucidated in both animal and human brains, and include local changes in cortical excitability (8, 9) and synaptic plasticity (10), with global modulation of cortical networks and functional connectivity (11, 12). Transcranial alternating current stimulation (tACS), a type of tES, has been demonstrated to modulate sleep architecture and cognitive performance when applied during SWA (7, 13). *Thus, we propose that application of tACS has the potential to improve sleep quality among patients with MCI, and to additionally improve measures of cognitive performance, mood, and quality of life.*

Hypotheses and Specific Aims: The purpose of this research is to investigate the utility of transcranial alternating current stimulation (tACS) to modulate sleep, cognition, mood, and quality of life among normal healthy adults, older adults, as well as individuals with mild cognitive impairment (MCI). We will do this with the following Specific Aims:

- 1). Optimize tACS parameters for duration, intensity and frequencies via utilization of EEG data recorded during tACS stimulation.
- 2). Determine whether recording artifacts introduced by tACS can confidently be removed from EEG signals.

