This will be a randomized-controlled trial with two study arms: a tACS treatment phase and a sham treatment phase. The subjects will be assigned to one of two treatment groups (tACS vs sham) in a 1:1 ratio using block randomization. Stimulation will be applied in-phase, single frequency or nested, if indicated based on the results of experiments 1 and 2. Computer-generated randomization will place each subject into one of the study groups. The primary outcome measured is EEG power of slow wave sleep of 0.5-2 Hz, measured immediately before and after each train of stimulation. To detect a significant change ($p<0.05$) of EEG power increase $\geq 20\%$ above sham, with a power of 0.80, a sample size of 30 subjects will be necessary. Subjects will receive either stimulation type, tACS or sham, each night for the one week study period, for up to 7 stimulation sessions pending results of Experiment 2. Subjects will have up to 24 weeks to complete all study sessions and complete the trial. The proposed study seeks to enroll 35 participants to account for participants that may fail our screening criteria, have unusable data or drop-out of the study before completion.

Secondary outcomes will include analysis of slow wave EEG coherence, slow and fast spindle activity, duration of slow wave sleep, total duration of sleep, and subjective sleep quality reported on the Consensus Sleep Diary (CSD), Pittsburgh Sleep Quality Index (PSQI), mood assessment by the Hospital Anxiety and Depression Scale (HADS), overall function in the Clinical Global Impression of Change (CGIC).

Consensus Sleep Diary (CSD)

The CSD is a sleep journal instrument that is designed to measure sleep and has been validated for intervention trials in insomnia (38, 41).

Word Paired-Associate Task

Our computerized paired-associate task consists of 48 semantically related words selected from a normative database with assessment of memory encoding on recollection performance (25, 42)

Finger Tapping Task

This is a finger sequence tapping task of procedural memory. Subjects repeatedly finger-tap with their non-dominant hand a five-element sequence presented on a computer monitor, e.g. 4-2-3-1-4, as fast and accurately as possible on a key board (7).

Pittsburgh Sleep Quality Index (PSQI)

This is a 10 question questionnaire consisting of questions related to usual sleep habits (39).

The Hospital Anxiety and Depression Scale (HADS)

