Inclusion Criteria- The subject population will be individuals between the ages of 51-85 who are native English speakers. We will further require older adult subjects to enroll in the study with a study partner to help them with the technological aspects of applying equipment and performing home-based cognitive assessments.

Exclusion Criteria-

- brain tumors
- skull defects
- epilepsy
- metal implants/devices above the neck
- eczema or sensitive skin
- severe insomnia that limits ability to sleep at night
- currently taking sedatives and/or sleeping medications
- sleep apnea that requires CPAP
- REM-sleep behavior disorder
- currently pregnant or trying to become pregnant during the study period
- diagnosis of cognitive impairment.

MCI subjects:

Inclusion Criteria- The subject population will be individuals between the ages of 45-90 who meet clinical criteria for diagnosis of amnestic MCI and are native English speakers. We will further require MCI patients enroll in the study with a study partner to help them with technological aspects of applying equipment and performing home-based cognitive assessments.

Exclusion Criteria-

- brain tumors
- skull defects
- epilepsy
- metal implants/devices above the neck
- eczema or sensitive skin
- severe insomnia that limits ability to sleep at night
- currently taking sedatives and/or sleeping medications
- sleep apnea that requires CPAP
- REM-sleep behavior disorder
- currently pregnant or trying to become pregnant during the study period

VII. VULNERABLE POPULATIONS

MCI individuals are considered a vulnerable population due to their cognitive impairment. They are the subject of this research study, and thus MCI individuals must be included. Subjects with diagnosis of MCI will be screened for decisional capacity via the UCSD Brief Assessment of Capacity to Consent (UBACC), and subjects who are found to have impaired capacity will require a legally authorized representative for consent (40).

VIII. RECRUITMENT METHODS

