Official Title: Application of Transcranial Alternating Current Stimulation for Modulation of Sleep and Cognitive Performance

NCT03112902

June 6th, 2021

Statistical Analysis Plan: For each arm, we will perform a three-arm cross-over design to determine whether there is a significant group difference between each tES condition as measured in EEG power in 0.5-2 Hz frequency following tES using repeated measures ANOVA. Recruitment of 15 subjects, with cross-over intervention (*sample size* 15) will allow us to detect differences between groups with an effect size of Cohen's  $d = 1.2$ , power of 80%, and significance of 0.05. This is based on sample sizes and effect sizes reported with motor network tES. Planned secondary analyses of each arm will include scores of slow wave EEG coherence, slow and fast spindle numbers, total duration of each sleep stage, changes in slow wave coherence, changes in slow wave power, self reported sleep timing changes, changes in anxiety and depression (measured by HADS), changes in clinical global impression of change (CGIC), and cognitive performance data, including assessment of procedural memory, verbal (declarative) memory encoding, attention/working memory/visuospatial processing using repeated measures ANOVA of the data.

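### MCI branch: sleep outcomes with no pre-treatment value are to be compared between two groups of about 15, aged 45 to 90, without age as a covariate; a prespecified age term is a cheap gain in precision

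*SAP*

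**What the plan says.** **Design of the MCI branch.** Protocol IV.5 states that subjects are "assigned to one of two treatment groups (tACS vs sham) in a 1:1 ratio using block randomization". It adds that "Subjects will receive either stimulation type, tACS or sham, each night for the one week study period". No subject is crossed to the other condition. The number judged necessary is 30, so about 15 per group, with 35 to be enrolled. No stratification by age is stated.

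**Population.** Protocol VI admits "individuals between the ages of 45-90 who meet clinical criteria for diagnosis of amnestic MCI". Age is an eligibility criterion, so it has to be known for every subject.

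**Schedule.** Protocol XII.5 lists seven home nights of stimulation and recording for MCI, with EEG gathered before and after stimulation. An adaptation night with EEG but no tACS is described only for the older-adult branch (IV.4 and XII.4).

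**Analysis.** The SAP names among its secondary outcomes "scores of slow wave EEG coherence, slow and fast spindle numbers, total duration of each sleep stage". It lists changes in slow wave coherence and in slow wave power as separate items. Everything is to be analysed by repeated measures ANOVA. No covariate is named, and the opening sentence describes a three-arm cross-over for every arm of the study.

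**Age.** Protocol I gives the motivation: impaired sleep, in particular fragmentation and "loss of slow wave activity (SWA) during non-rapid-eye-movement (NREM) sleep, is known to occur during the physiologic process of aging".

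**The concern.** In the cross-over branches each subject serves as their own control, so age drops out of the treatment contrast. In the MCI branch as the protocol describes it, treatment is compared between people, and those people may differ in age by up to 45 years. The duration of a sleep stage over a whole night has no pre-treatment counterpart, because no untreated night is scheduled. Seven nights per subject do not help here: averaging over nights reduces night-to-night noise, but age is constant within a subject, so its contribution stays in the between-subject error.

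Two things follow. Any age-related variation widens the confidence interval for the tACS effect on sleep architecture. And a chance difference in mean age between two groups of about 15 moves the estimate in that particular trial. Aims 4 and 5, which concern sleep architecture and the viability of treatment in MCI, draw on these outcomes. Age is already in hand, so both effects can be reduced without collecting anything new.

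**Working it through.** **1. The plan's own figure.** Protocol IV.5 gives 30 subjects for an increase of at least 20% over sham, 80% power, p < 0.05. No SD is given, so the figure cannot be reproduced; it can only be inverted. With 15 per group, two-sided 0.05 (sidedness is not stated), the detectable standardised difference is

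(1.960 + 0.842) × √(2/15) = 1.02 by the normal approximation, or 1.06 with the t distribution on 28 df.

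This would imply an SD of 20/1.02 = 19.6 or 20/1.06 = 18.9 percentage points. The SAP's d = 1.2 is stated for 15 subjects in a cross-over, so it does not size this comparison. The value 1.06 is used below as an effect with exactly 80% unadjusted power.

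**2. Effect of adding age.** Let r be the within-group correlation between age and the outcome analysed. The documents do not give r, so it is an assumption, shown over a range. Adding age multiplies the residual variance by (1 − r²). Estimating the age slope costs a factor of 1 + 1/26 on average (26 = 30 − 4) and one df (27 instead of 28). The variance ratio, adjusted to unadjusted, is (1 − r²) × (1 + 1/26).

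| r | variance ratio | change | power at d = 1.06 | detectable d at 80% |
|---|---|---|---|---|
| 0 | 1.000 × 1.038 = 1.038 | +4% | 78.4% | 1.08 |
| 0.2 | 0.960 × 1.038 = 0.997 | 0% | 80.0% | 1.06 |
| 0.3 | 0.910 × 1.038 = 0.945 | −5% | 82.1% | 1.03 |
| 0.4 | 0.840 × 1.038 = 0.872 | −13% | 85.0% | 0.99 |
| 0.5 | 0.750 × 1.038 = 0.779 | −22% | 88.7% | 0.94 |

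Break-even is where (1 − r²)(27/26) = 1, that is r² = 1/27, r = 0.19. At r = 0.5 the adjusted analysis is worth an unadjusted trial of 30/0.779 = 38.5, or about 38 subjects.

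**3. Chance imbalance.** The difference in mean age has standard error √(2/15) = 0.365 SD of age. One trial in five exceeds 1.2816 × 0.365 = 0.468 SD in absolute value. A gap of that size shifts the unadjusted difference by 0.468 × r: 0.14 SD of the outcome at r = 0.3 and 0.23 SD at r = 0.5.

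In years this depends on the age SD, which the documents do not give. If ages were uniform over 45 to 90 (a wide case), the SD is 45/√12 = 13.0 and the standard error is 13.0 × 0.365 = 4.7 years. The chance of a gap above 5 years is then about 29%. With an assumed SD of 8 to 12 years, the one-in-five gap is 3.7 to 5.6 years.

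**4. Which outcomes are affected.**
- *Stage durations* are totals for the night. No untreated night exists in MCI, so they have no pre-treatment value.
- *Spindle numbers* are not tied to a window in the SAP. If counted over the night they are in the same position; if counted around stimulation trains they have a pre-stimulation value.
- *Slow wave coherence and power* can be measured before stimulation, and their changes are listed separately in the SAP. The subject's own earlier value is then the natural covariate.

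**The case against.** **The SAP does not state an unadjusted between-group comparison.** It states a cross-over, in which age would cancel, and Protocol IV.5 itself calls the two arms phases. This stands as far as it goes: the design conflict is the first thing to settle. But the protocol's allocation and treatment sentences describe a parallel trial. Once the SAP is brought into line, a between-group model has to be written, and age belongs in that decision.

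**The protocol does not say age drives these outcomes.** A reader might infer that it does. Protocol I ties ageing to fragmented sleep and loss of slow wave activity. That supports stage durations by inference, but it says nothing of coherence or spindles. The protocol also links sleep disruption to MCI and its pathology, so the age correlation within an amnestic MCI group is unknown. This stands.

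**Randomisation already deals with chance imbalance.** Also correct. A reader might infer bias, or that an age difference would pass for a tACS effect. The unadjusted estimate is unbiased and its 5% error rate already allows for such imbalance. The shifts of 0.14 to 0.23 SD are about 0.4 to 0.6 of the standard error of the treatment difference (0.365 SD).

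**The gain is assumed.** It is nil at r near 0.2, two points of power at r = 0.3, and material only from about r = 0.4. This limits the weight of the point. It does not remove it, because the possible loss is small.

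**The stakes are modest.** These are secondary outcomes in work intended to generate pilot data, and the MCI primary outcome is measured before and after each train. Nor is this the smallest comparison by number of subjects: the cross-over branches need 15, the MCI branch 30.

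**Conclusion.** The point holds as a cheap improvement to secondary analyses in the MCI branch, not as an error that invalidates them. It is strongest for sleep-stage durations, conditional for spindle numbers, and does not apply to outcomes that carry their own pre-stimulation value. It rests on reading the MCI branch as parallel, as Protocol IV.5 describes it, with about 15 analysed per group.

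The size depends on r, which neither document supplies: about 5% to 22% less variance for r between 0.3 and 0.5, nothing near 0.2, and about 4% more variance if age is unrelated to the outcome. That worst case takes power from 80.0% to 78.4%. The documents do not support a claim of bias, an invalid test, or an established age effect on coherence or spindles.

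**What to change.** 1. Reconcile the SAP's description of the MCI branch with Protocol IV.5, so that one design is stated.
2. If it is parallel, state for MCI stage durations, and for any other level outcome without a pre-stimulation value, a between-group ANCOVA on the subject's mean over nights, or a mixed model over nights with subject as a random effect. Include treatment group and age at enrolment as a prespecified continuous covariate.
3. State the window in which spindles and coherence are scored. Where a pre-stimulation value exists, adjust for that value instead of age. Say which one is used: only the value before the first train of the first night is wholly untreated.
4. Report the unadjusted comparison as supportive.

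The cost is a few sentences in the SAP and one degree of freedom, with no new data. Fixing the covariate in advance also prevents a choice made after the results are seen.

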Total time		60 minutes

HOME PORTION- ADAPTATION NIGHT

Name of Instrument/tool/procedure	Purpose (i.e. what data is being collected)	Time to complete
EEG Recording	Gather EEG data before and after stimulation	overnight
Complete Consensus Sleep Diary	Assess Sleep Quality (after each night of study)	10 minutes
Total time		Overnight

HOME PORTIONS-tACS TREATMENT NIGHTS

Name of Instrument/tool/procedure	Purpose (i.e. what data is being collected)	Time to complete
tACS/EEG Stimulation and Recording	Gather EEG data before and after stimulation	overnight
Complete Consensus Sleep Diary	Assess Sleep Quality (after each night of study)	10 minutes
Word Paired-Associate Task	Assess Memory Encoding (before and after sleep)	20 minutes
Finger Tapping Task	Assess Procedural Memory (before and after sleep)	15 minutes
Total time		Overnight x 3 nights (1 week apart for washout)

VISITS TWO, FOUR, and SIX

Name of Instrument/tool/procedure	Purpose (i.e. what data is being collected)	Time to complete
Post-procedure questionnaire	Assess for tolerability of device and address any safety concerns	15 minutes
Collection of Sleep Diary and Equipment	Collect and Inventory Instruments and Hardware	15 minutes
Total time		30 minutes

VISITS THREE, and FIVE

Name of Instrument/tool/procedure	Purpose (i.e. what data is being collected)	Time to complete
EEG/tACS Equipment Distribution	Ensure subjects remember proper equipment use	20 minutes
Total time		20 minutes

5. tACS SLEEP MODULATION MCI EXPERIMENT

INITIAL VISIT

Name of Instrument/tool/procedure	Purpose (i.e. what data is being collected)	Time to complete
Gather informed consent/UBACC	Gather consent/Screen for capacity	15 minutes
EEG/tACS Equipment Trial	Teach subjects proper equipment use/adjust for comfort	45 minutes
HADS	Assess anxiety and depression (to be administered for MCI trial)	5 minutes
CGIC	Assess Global Impression (to be administered for MCI trial)	5 minutes
Total time		60-70 minutes

HOME PORTIONS

Name of Instrument/tool/procedure	Purpose (i.e. what data is being collected)	Time to complete
tDCS/EEG Stimulation and Recording	Gather EEG data before and after stimulation	overnight
Complete Consensus Sleep Diary	Assess Sleep Quality (after each night of study)	10 minutes

Word Paired-Associate Task	Assess Memory Encoding (before and after sleep each night)	20 minutes
Finger Tapping Task	Assess Procedural Memory (before and after sleep)	15 minutes
Total time		Overnight x 7 nights

VISITS TWO, FOUR and SIX

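### The HADS analysis in the MCI branch works on changes and does not adjust for the initial-visit score already collected; adjusting would cost almost nothing and may gain some precision

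*SAP*

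**What the plan says.** The SAP is a single paragraph. Its secondary analyses include "changes in anxiety and depression (measured by HADS"), and the list closes with "attention/working memory/visuospatial processing using repeated measures ANOVA of the data". It defines no change score, time factor or contrast, and names no covariate.

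The protocol uses HADS in one branch only. Section IV.5 (MCI subjects) gives as a secondary outcome "mood assessment by the Hospital Anxiety and Depression Scale (HADS"). Section XII.5 schedules it at the initial visit, before the home nights, and again in the table for visits two, four and six, each time with the purpose "Assess anxiety and depression (to be administered for MCI trial").

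On design, Section IV.5 assigns MCI subjects to tACS or sham "in a 1:1 ratio using block randomization" and continues: "Subjects will receive either stimulation type, tACS or sham, each night for the one week study period". It states that "a sample size of 30 subjects will be necessary". The SAP instead opens with "For each arm, we will perform a three-arm cross-over design", which does not fit that description.

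**The concern.** In a randomised two-group comparison with a pre-treatment measurement of the same scale, there are two common ways to use that measurement. One subtracts it and compares changes. The other keeps the follow-up score as outcome and puts the initial score in the model as a covariate. With one initial and one follow-up score, the group-by-time test of a repeated measures ANOVA is the change-score comparison, so naming that method does not supply the adjustment.

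Subtraction fixes the slope on the initial score at 1. With equal SDs the best slope is the correlation r, which is below 1. If the arms differ by chance at the start, the change score therefore removes too much of that difference. The cost is precision. Mood is part of the hypothesis in Section I of the protocol, and HADS is the instrument named for it. The branch is small, and one of the study's aims is to supply pilot data for larger trials, so a more precise estimate would be useful.

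**Working it through.** **Plan's own figure.** There is none to reproduce: neither document gives a sample size, SD, correlation or power for HADS. The SAP's 15 subjects at d = 1.2 concern EEG power and are not used here.

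**Inputs**
- 30 subjects needed, allocated 1:1, hence 15 per arm (Protocol IV.5).
- One initial score and one follow-up score with equal SD, set to 1 (assumed).
- Correlation r between them: not in the documents; 0.3 to 0.95 assumed.
- Two-sided 5% test (the SAP gives 0.05 without stating sidedness).

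**Formulas**
- Change score: variance proportional to 2(1 − r).
- Baseline-adjusted (ANCOVA): variance proportional to 1 − r².
- Large-sample ratio: (1 − r²) / [2(1 − r)] = (1 + r)/2.
- With N = 30 the slope must be estimated, which multiplies the ratio by (N − 3)/(N − 4) = 27/26 = 1.038.

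**Power.** With 28 degrees of freedom the change analysis has 80% power at a noncentrality of 2.902. The adjusted analysis then has noncentrality 2.902/√(ratio at N = 30) with 27 degrees of freedom.

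| r (assumed) | 2(1 − r) | 1 − r² | Ratio, large sample | Ratio, N = 30 | Power of adjusted analysis where change has 80% |
|---|---|---|---|---|---|
| 0.3 | 1.40 | 0.910 | 0.650 | 0.68 | 93% |
| 0.5 | 1.00 | 0.750 | 0.750 | 0.78 | 89% |
| 0.7 | 0.60 | 0.510 | 0.850 | 0.88 | 85% |
| 0.8 | 0.40 | 0.360 | 0.900 | 0.93 | 82% |
| 0.9 | 0.20 | 0.190 | 0.950 | 0.99 | 80% |
| 0.95 | 0.10 | 0.0975 | 0.975 | 1.01 | 79% |

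**Break-even.** (1 + r)/2 × 27/26 = 1 gives r = 25/27 = 0.93. Above that the adjusted estimate is very slightly worse, by about 1% of variance at r = 0.95.

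**Simulation.** With 20,000 trials per value, the variance ratios were 0.781, 0.881 and 0.985 at r = 0.5, 0.7 and 0.9, in agreement with the formula.

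**Chance imbalance.** At 15 per arm the difference in mean initial score has a standard error of √(2/15) = 0.37 SD. For an imbalance of that size the change score over-corrects by (1 − r) × 0.37, which is 0.18 SD at r = 0.5.

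**Several follow-ups.** The protocol lists three later HADS visits. If their mean is analysed and all correlations equal r, the change variance is proportional to 4(1 − r)/3 and the adjusted variance to (1 − r)(1 + 3r)/3. The large-sample ratio is (1 + 3r)/4, that is 0.625 at r = 0.5 and 0.775 at r = 0.7. The single-follow-up table therefore does not overstate the gain for an averaged analysis under that assumption.

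**The case against.** The strongest objection is that the design under which HADS would be analysed is not settled. The SAP, the later document, describes a three-arm cross-over throughout. Under a cross-over HADS would be compared within subject, and neither 15 per arm nor the ratios above would apply. The protocol is not wholly clean either: Section IV.5 also speaks of a treatment phase and a sham phase, and the MCI visit tables repeat the collection and redistribution visits of the cross-over branches. This stands as a reason to reconcile the documents first. It does not remove the point, because the 1:1 allocation and the statement that each subject receives one stimulation type for the week make parallel groups the better reading.

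Second, the SAP defines no contrast. A reader might infer that the sponsor deliberately chose a change-score estimator. The wording does not support that: it mentions changes and a broad method, and the model is largely unspecified. With the initial visit and three later ones, the group-by-time test would also be a 3-degree-of-freedom interaction, not a single change comparison. What stands is that no adjustment for the initial score is planned under any reading.

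Third, r may be high over about one week of treatment, and then the gain disappears. That is correct, and the table shows it.

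**Conclusion.** The point holds as a modest matter of precision for one secondary outcome. At 15 per arm with one follow-up, adjustment reduces the variance by about 32% at r = 0.3, 22% at 0.5, 12% at 0.7, 7% at 0.8 and 1% at 0.9, with nothing gained above about 0.93. This rests on parallel groups, equal SDs and an assumed r. Since the worst loss shown is about 1% of variance, adjustment is the better default without knowing r.

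Three stronger readings are not supported. A reader might infer that the planned HADS comparison is biased; under randomisation both estimators are unbiased. A reader might infer that the change score is always less precise; at this sample size that fails for very high r. And a reader might carry the point over to the EEG endpoint or the study's stated power; the calculation concerns HADS only, for which no power is claimed. The severity is low: a free improvement.

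**What to change.** Two edits to the SAP, made together:

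1. State that the MCI branch is analysed as the parallel two-group comparison of tACS and sham described in Protocol Section IV.5, and reconcile the blanket cross-over wording with it.
2. State that the HADS anxiety and depression scores are each compared between tACS and sham with the initial-visit score as covariate, either by ANCOVA at one named post-treatment visit or by a mixed model over the post-treatment visits. Change from the initial visit may be shown descriptively.

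The second edit must name the visit or visits, because HADS is scheduled at three of them after the initial one. The cost is one degree of freedom and no new data, with a variance loss of about 1% if r turns out to be very high.

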The subjects will be assigned to one of three treatment groups (tACS nested, tACS single frequency, or sham) using block randomization. Computer-generated randomization will place each subject into one of the study groups initially, then cross each subject the each other condition subsequent sessions. The primary outcome measure is induced EEG power of slow wave sleep of 0.5-2 Hz measured immediately before and after each train of stimulation. To detect a significant change ($p<0.05$) of EEG power increase $\geq 20\%$ above sham, with a power of 0.80, a sample size of 15 subjects will be necessary, based on effect sizes from prior studies (7). Subjects will receive 1 session for each stimulation type, in a cross-over design with at least 1 week between each stimulation condition for wash-out. This will total to 3 sessions for each subject, with a total of 45 sessions for all subjects. Subjects will have up to 24 weeks to complete all study sessions and complete the trial. The proposed study seeks to enroll 30 participants to account for participants that may fail our screening criteria, have unusable data or drop-out of the study before completion. Secondary outcomes will include analysis of slow wave EEG coherence, sleep spindle signal, duration of slow wave sleep, total duration of sleep, word-paired associates task and finger tapping task (7, 25), as well as subjective sleep quality reported on the Consensus Sleep Diary and Pittsburgh Sleep Quality Index (38, 39). Data collection for this study is expected to take 6 months.

4. Assessment of tACS in Older Adult Subjects: In this branch of our study, we will test older adults for response to tACS applied during NREM sleep, with outcomes of EEG data, cognitive performance assessments, as well as assessment of sleep quality, mood, and quality of life measures. In addition, subjects will be screened for decisional capacity via the UCSD Brief Assessment of Capacity to Consent (UBACC), and subjects who are found to have impaired capacity will require a legally authorized representative for consent (40).

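### Repeated measures ANOVA as the only method discards usable home nights in the 18-50 cross-over, and for MCI the SAP leaves open whether one bad night removes a subject

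*SAP*

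**What the plan says.** The SAP is a single paragraph. Its primary analysis asks "whether there is a significant group difference between each tES condition" in 0.5-2 Hz EEG power, by repeated measures ANOVA in a three-arm cross-over said to apply to each arm. The secondary analyses are also done "using repeated measures ANOVA of the data". The sample size statement reads "Recruitment of 15 subjects, with cross-over intervention". The SAP has no rule for unusable nights, no minimum number of usable nights, no imputation and no mixed model.

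The protocol (section IV, branches 3, 4 and 5) enrols more subjects than it needs "to account for participants that may fail our screening criteria, have unusable data or drop-out of the study before completion":

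- 18-50 branch: 30 enrolled for 15 needed, three conditions, one night each.
- Older adults: 35 enrolled for 15 needed, two conditions, one night each.
- MCI: 35 enrolled for 30 needed ("with a power of 0.80, a sample size of 30 subjects will be necessary"), two parallel groups 1:1, stimulation "each night for the one week study period, for up to 7 stimulation sessions pending results of Experiment 2". The procedures table in section XII lists seven nights.

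Recording takes place in subjects' homes (section XII, Location). Section XV excludes the data of subjects who withdraw, but does not cover a subject who completes the study with one unusable night.

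**The concern.** In its classical form, repeated measures ANOVA works on a complete subject-by-level table. A subject missing one cell leaves the analysis, and so do that subject's good nights. In the 18-50 branch, a subject with usable nested and sham nights but a failed single-frequency night adds nothing to the nested-sham comparison. Valid data are lost, and the analysed group is selected for technically clean recordings.

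In MCI the problem is of another kind. Each subject receives only one condition, so condition cannot be the repeated factor and the SAP's design does not fit. Night is a natural candidate, since Aim 4 concerns cumulative effects over consecutive nights, but the SAP does not say so. Two analysts could follow the SAP and analyse different sets of MCI subjects, and the choice could be made after the data are seen.

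**Working it through.** **The plan's own figures.** The MCI figure of 30 cannot be rebuilt, because no standard deviation or standardised effect accompanies the 20% increase. A two-sided two-sample t-test at 0.05 with 15 per arm has 80% power at d = 1.06, and that value serves as the reference below. The SAP's 15 subjects at d = 1.2 and 80% can be matched by a three-level repeated measures ANOVA, taking d as the range of equally spaced means with zero within-subject correlation. The noncentrality is then 15 x (0.6² + 0 + 0.6²) = 10.8 on 2 and 28 degrees of freedom, and power is 80.2%. Those assumptions are not in the documents.

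**Assumption.** Neither document gives a night-failure rate. Let q be the share of nights that fail, at first independently. Then a subject with k required nights is complete with probability (1-q)^k.

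**18-50 branch (k = 3, 30 enrolled, 15 needed), q = 10%.**
- Complete subjects: 0.9³ = 0.729, or 30 x 0.729 = 21.9.
- Subjects with both nights of any one pair: 0.9² = 0.81.
- Standard error of a pairwise contrast from complete cases, relative to all available pairs: √(0.81/0.729) = 1.054.
- Expected completers reach 15 at q = 1 - (15/30)^(1/3) = 20.6%, before other losses.

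**Older adults (k = 2, 35 enrolled, 15 needed).**
- At q = 10%: 35 x 0.81 = 28.4 complete.
- Expected completers reach 15 at q = 1 - (15/35)^(1/2) = 34.5%, before other losses.
- There is only one pair of conditions, so a subject with one usable night has no within-subject contrast to recover.

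**MCI, only if all seven nights are required (k = 7, 35 enrolled, 30 needed).**
- Break-even: q = 1 - (30/35)^(1/7) = 2.18%.
- Power for d = 1.06, with completers split equally between arms and all 35 subjects otherwise retained:

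| q | Expected completers, 35 x (1-q)^7 | Power |
|---|---|---|
| 2% | 30.4 | 81% |
| 5% | 24.4 | 71% |
| 10% | 16.7 | 53% |

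- The surplus of five must also cover screen failures and drop-outs. If these take 1, 2 or 3 subjects, the break-even falls to 1.8%, 1.4% or 0.9%.
- With fewer required nights the break-even rises: 3.0% for five nights, 5.0% for three.
- If each subject's usable nights are averaged instead, a subject is lost only when all seven fail: 0.1^7, or 1 in 10 million, at q = 10%.

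**Clustered failures in MCI, same all-seven-nights rule.** A beta-binomial model with an assumed within-subject correlation gives:

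| Correlation | Break-even q | Completers of 35 at q = 10% |
|---|---|---|
| 0 | 2.2% | 16.7 |
| 0.1 | 2.8% | 19.9 |
| 0.3 | 4.2% | 24.0 |
| 0.5 | 5.8% | 26.8 |

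**The case against.** The strongest reply is that the large MCI figures rest on a model nobody wrote down. The SAP compares conditions, condition in MCI is between subjects, and the number of sessions is not fixed. EEG power is measured around each stimulation train, so some summary over trains is needed anyway, and a mean over usable nights fits the text as well as a seven-level night factor does. This stands. A reader might infer that MCI falls short of 30 as soon as about 2% of nights fail. The documents do not support that as an unconditional statement, because they do not make night a factor, require all seven nights or say that incomplete subjects are dropped.

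A reader might also infer that power in the cross-over branches falls below 80%. That is not shown. The surplus there is meant partly for unusable data, and at 10% failed nights both branches keep well over 15 complete subjects.

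A third tempting figure is 45% power in MCI at 10% failed nights. It starts from 30 subjects (30 x 0.9^7 = 14.3, about 7 per arm) and so assumes that the five surplus subjects are already lost to other causes. From 35 it is about 53%.

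Independent failure is unfavourable to the plan. Poor equipment fit or tolerance would plausibly cause repeated failures in the same subject, which leaves more complete subjects at the same rate. This also stands.

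What the reply does not remove is the gap itself. The only named method drops incomplete subjects in the cross-over branches, and the SAP offers no alternative for MCI.

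**Conclusion.** The point holds in a limited form. In the 18-50 branch, followed as written, the method loses usable pairs. The cost is modest: about 5% in standard error at an assumed 10% of nights failing independently, with the target of 15 met until about 21% fail before other losses. In older adults the target survives to about 35%, and a mixed model gains little.

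In MCI the finding is an unstated model with a potentially large consequence. If all seven nights are required, expected completers drop below 30 above about 2.2% failed nights. Falling just short of 30 costs little power; the loss becomes material from about 5%. If usable nights are averaged, almost nothing is lost.

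All failure rates are assumptions, and d = 1.06 is a reference value that the documents do not tie to the 20% increase. The change is worth making because it is cheap and settles the analysed set in advance.

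**What to change.** In the cross-over branches, replace repeated measures ANOVA with a linear mixed model fitted by REML to all usable nights, with a random subject effect, condition fixed and small-sample degrees of freedom such as Kenward-Roger. This is valid under missing at random and uses subjects with partial data.

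For MCI, state the model. Either fit nights within subject with an arm effect, or analyse an equivalent subject mean over usable nights with a stated minimum number of nights. Define an unusable night before unblinding, and support the enrolment surplus with an assumed night-failure rate.

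Keep the complete-case repeated measures ANOVA as a sensitivity analysis where the design allows it.

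The cost is a few sentences in the SAP and slightly more programming. The downside is reliance on a covariance model, which is small with two or three nights per subject and needs more thought with seven.
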